| Person who directs and monitors the research | [name] | |
| Title | Study of the determinants of successful decanulation in tracheostomized patients in the post-intensive care unit. A cohort study | |
| Acronym | DESCATRON | |
| Protocol version | n° of 14/01/2021 | |
| Rationale / context | The success factors for decanulation are not well known in the literature and the decision to decanulate is mainly based on clinical judgment. The failure rate of decanulation is between 2 and 25% with a poor prognosis in case of failure. | |
| Main Objective | To determine the factors associated with successful decanulation in tracheostomised patients admitted to Difficult-to-Wean Unit. | |
| Secondary objectives The secondary objectives are to evaluate in tracheostomized hospitalized in Difficult-to-Wean Unit.: -The prevalence of successful decanulation ; -The prevalence of successful weaning from invasive ventilation; -Factors associated with successful weaning from invasive ventilation (VI | | |
| | -Demographic characteristics of these patients at admission; | |
| | -The ventilatory characteristics of these patients at admission; | |
| | -Biological characteristics of these patients at admission; | |
| Research scheme | Prospective, monocentric, interventional cohort study with minimal risks and constraints falling under 2° of article L.1121-1 of the Public Health Code. | |
| Inclusion criteria | -Admission to Difficult-to-Wean Unit at Forcilles Hospital; | |
| | -Presence of a tracheotomy on admission to DIFFICULT-TO-WEAN UNIT; | |
| | -Presence of invasive ventilation on admission to DIFFICULT-TO-WEAN UNIT with a predicted duration of > 48 hours; | |
| | -Patient aged at least 18 years at the time of inclusion; | |
| | -Affiliation to or beneficiary of a social security scheme; | |
| | -Oral, free, informed and express consent of the patient or a relative. | |
| Non-inclusion criteria | -Known pregnancy ; -Person subject to a legal protection measure; -Person under guardianship or curatorship; -Refusal of access to data by the patient or the designated trusted person. | |
| Primary endpoint | Factors potentially associated with successful decanulation will be collected prospectively: -Severity factors related to the ICU stay; | |
| | | |

| -Ventilatory factors; |
|---|
| - |
| -Respiratory factors; |
| -Extra-respiratory factors; |
| -Proportion of successful decanulation among all included patients; |
| -Proportion of successful weaning from IV among all included patients; |
| -Collection of biological parameters within the first 48 hours of admission to DIFFICULT-TO-WEAN UNIT; |
| -Ventilatory parameters on admission to DIFFICULT-TO-WEAN UNIT; |
| -Demographic characteristics of these patients during DIFFICULT-TO-WEAN UNIT hospitalisation: mortality, duration of hospitalisation, duration of invasive ventilation. |
| -Nutritional status. |
| None |
| 100 |
| 1 |
| 25 months |
| Univariate comparisons will use the usual statistical tests after verification of the |
| distribution of the variables (Chi2 or Fisher's test, t-test, anova or their non- |
| parametric equivalents Wilcoxon and Kruskal-Wallis tests). The variables will be |
| compared between the 2 groups (failure or success of decanulation) by the |
| appropriate tests according to the type of variables (quantitative or qualitative) |
| and their distribution. The selection of variables in the prediction model will be |
| done by multivariate logistic regression based on AIC. |
| Useful information for post-ICU settings follow-up and for prioritising or not early rehabilitation in these patients with prolonged stays in intensive care with tracheostomy. |
| Hôpital Forcilles |
| None |
| Hôpital Forcilles-Fondation Cognacq-Jay |
| |

Table des matières

| KE | KEY CONTACTS | | | | |
|----|--------------|---|----|--|--|
| PF | ROTO | COL VERSION HISTORY | 3 | | |
| SL | JMMA | ARY OF THE RESEARCH | 4 | | |
| 1 | Rat | tionnal | 9 | | |
| 2 | Нур | pothèse de recherche | 10 | | |
| 3 | Obj | jectives | 10 | | |
| | 3.1 | Main Objective | 10 | | |
| | 3.2 | Secondary objectives | 10 | | |
| 4 | Out | tcome | 11 | | |
| | 4.1 | Main outcome | 11 | | |
| | 4.2 | Secondary outcomes | 12 | | |
| 5 | Pat | tient selection | 13 | | |
| | 5.1 | Inclusion criteria | 13 | | |
| | 5.2 | Non-inclusion criteria | 13 | | |
| | 5.3 | Recruitment procedures | 13 | | |
| 6 | Res | search design | 14 | | |
| | 6.1 | Type of study | 14 | | |
| | 6.2 | Outline of the research | 14 | | |
| | 6.3 | Provisional timetable for the research | 14 | | |
| 7 | Des | scription of the usual post-ICU settings management | 15 | | |
| | 7.1 | Medical and nursing procedures | 15 | | |
| | 7.2 | Weaning from mechanical ventilation | 15 | | |
| | 7.3 | Early rehabilitation | 16 | | |
| | 7.4 | ICU-acquired muscle weakness assessment | 16 | | |
| | 7.5 | Assessment of swallowing disorders | 16 | | |

Invasive mechanical ventilation after tracheal intubation is a common ICU procedure to treat patients with acute respiratory failure.

However, even if the acute event is resolved, the length of stay in the ICU may be prolonged by the maintenance of prolonged mechanical ventilation. There are many factors that contribute to the maintenance of prolonged mechanical ventilation and prevent progress in weaning from the ventilator: curarisation, lung infections, pre-existing respiratory disease etc (1).

It has been shown that a delay in weaning is associated with a higher rate of complications in the ICU, an increase in the length of stay due to increased neuromyopathy and nutritional disorders (undernutrition, swallowing disorders) as well as a decrease in survival in the ICU (2)(3).

In case of prolonged invasive ventilation, after several failed weaning and re-intubation (4), these patients are therefore most often tracheotomised by percutaneous or surgical means in order to advance in ventilatory weaning.

The evolution of these tracheostomised patients is long and the difficulties of weaning from mechanical ventilation in this population are partly linked to the lack of professional means allowing satisfactory rehabilitation before decanulation (5).

The weaning units, initially created in the United States (6), then in France from the beginning of the 2000s, have improved the success rate of weaning in these patients.

The challenge of tracheal decanulation remains the ultimate goal in these patients. Several studies have shown the interest of a multidisciplinary management of these patients: physicians, physiotherapists, speech therapists, nurses etc. with their own role in the different stages of weaning and decanulation (7)(8)(9)(10).

The stages of the decanulation process are described in a few studies: switching to spontaneous ventilation without occasional mechanical assistance, repeated spontaneous ventilation sessions during the day, daytime spontaneous ventilation, daytime and nighttime spontaneous ventilation with, in parallel with these progressive sessions, a resumption of speech and swallowing (10)(11)(12)(13).

The factors for successful decanulation are not well known in the literature and the decision to decanulate is mainly based on clinical judgement: weaning from mechanical ventilation, normal nausea reflex, effective cough, ability to swallow secretions, correct saturation SaO2>90% for more than 24 hours (14).

The failure rate of decanulation is between 2 and 25% (15)(16) with a poor prognosis in case of failure (17).

Thus, the determination of the success factors for decanulation of tracheostomised patients is a major challenge to select and optimise the management of these patients.

2 Hypothèse de recherche

The severity of the resuscitated patient, factors related to invasive ventilation, respiratory and extra-respiratory status are independent factors for successful decanulation.

3 Objectives

3.1 Main Objective

The main objective is to determine the factors associated with successful decanulation in tracheostomised patients admitted to the Difficult-to-Wean Unit.

3.2 Secondary objectives

The secondary objectives are to evaluate in tracheostomized patients hospitalized in Difficultto-Wean Unit:

- The prevalence of successful decanulation ;
- The prevalence of successful weaning from invasive ventilation;
- Factors associated with successful weaning from invasive ventilation (VI);
- Demographic characteristics of these patients at admission;
- The ventilatory characteristics of these patients at admission;
- Biological characteristics of these patients at admission;
- The nutritional status of these patients at admission.

4 Outcome

4.1 Main outcome

Successful decanulation is defined as maintenance of spontaneous ventilation in the absence of recanulation, acute use of non-invasive ventilation (NIV) or death within 48 hours.

Factors potentially associated with successful decanulation will be collected prospectively:

- Severity factors related to the ICU stay:

o Total number of oro-tracheal intubations ;

o Number of days on mechanical ventilation;

o Curarisation or not with duration

o Whether or not prone sessions were performed with duration;

o Whether or not ECMO was used as a back-up;

o Number of pneumopathies acquired under mechanical ventilation;

o IGS2 ;

- Ventilatory factors :

o Number of failed extubations before tracheostomy in the ICU;

o Duration of mechanical ventilation before tracheostomy in the ICU (days);

o Type of tracheostomy used: percutaneous or surgical;

o Time to first attempt at Difficult-to-Wean Unit de-ventilation (days);

o Time to 24-hour at Difficult-to-Wean Unit de-ventilation (days);

o Time from 24-hour deventilation to successful DIFFICULT-TO-WEAN UNIT decanulation (days);

o Number of ventilator-associated lung diseases (VAPs) in at Difficult-to-Wean Unit;

- Respiratory factors:

o Ultrasound lung ventilation score on admission to at Difficult-to-Wean Unit;

o Diaphragmatic dysfunction on admission to at Difficult-to-Wean Unit;

o Bronchial fibroscopy abnormalities prior to decanulation;

- Extra-respiratory factors:

o Confusional state on admission to at Difficult-to-Wean Unit (CAM-ICU, Appendix 1);

o Existing swallowing disorders (assessed after 6 hours of ventilation) by the modified Cowling swallowing score (18);

o Oral status on admission to at Difficult-to-Wean Unit (normal, moderately impaired, dilapidated, no teeth);

o ICU-Acquired muscle weakness (MRC score) on admission to at Difficult-to-Wean Unit;

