9.2.2 Data collection at inclusion

At the inclusion visit, the following data will be collected from the patient's computerised medical record, or directly from the patient or relative if data is missing:

- Age, sex (male/female), weight, height, body mass index (BMI);

Medical history: chronic heart disease (hypertension, coronary artery disease, dyslipidaemia, rhythm disorder), diabetes, chronic respiratory disease (Chronic Obstructive Pulmonary Disease (COPD), Sleep Apnoea Hypopnoea Syndrome (SAHOS), neurological disease, cancer, chronic renal failure, smoking (active, weaned, no), chronic alcoholism (yes, no);
 Data related to the initial ICU stay:

o Type of intensive care unit (medical, surgical, polyvalent) and type of institution (public, private non-profit, private);

o Reason for admission to intensive care: acute respiratory failure (ARF), ARF on chronic respiratory failure (CRF), cardiogenic shock, septic shock, haemorrhagic shock, polytrauma, post-operative, cardiorespiratory arrest (CRA), stroke, burns, pancreatitis, coma;

o IGS2 score on initial admission to the ICU.

- Number of failed extubations;
- Total duration of oro-tracheal intubation before tracheostomy (days);
- Number of VAPs (days);
- Performance of prone sessions (yes/no);
- If applicable, total duration of prone position (days);
- Use of ECMO support (veno-venous/arteriovenous/no);
- Tracheostomy performed (percutaneous/surgical/not);
- Resuscitation neuromyopathy (yes/no);

- Presence of BMR/BHR (yes/no);

- Limitation and discontinuation of active therapies (LATA) in the ICU (yes/no);

- Length of stay in intensive care (days);

- Type of tracheostomy cannula: uncuffed fenestrated, cuffed fenestrated, uncuffed non fenestrated;

- Cannula model (Shiley/Bivona/Trachoe/Other);

- Presence of mechanical ventilation (yes/no) and parameters:

o Mode: Controlled/PS/Other

o PS, PEEP, Vt, HR

o FiO2 (%)

- Biological check-up on admission within 48 hours of admission to DIFFICULT-TO-WEAN UNIT: haemoglobin, leucocytes, lymphocytes, neutrophils, troponin, renal function (urea, creatinine, GFR), metabolic function (calcium, magnesium, phosphate, TSH, cortisol at 8 hours, 25(OH)D) and inflammatory function (albumin, CRP);

- MRC score;

- Pulmonary ultrasound ;

- Diaphragmatic ultrasound;
- Confusional state by CAM-ICU (yes/no) (Appendix);
- Oral status (normal/moderate impairment/decay/no teeth);
- Vocal status (normal/minimal alteration/severe alteration/absence);

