10.3 Main objective

Patients will be classified into 2 groups: success or failure of decanulation. The variables collected will be compared between the 2 groups by the appropriate tests according to the type of variables (quantitative or qualitative) and their distribution. The results of these comparisons will be used to select the variables showing a difference between the 2 groups (p < 0.20) for inclusion in the multivariate logistic regression. (24)(25)

The previously selected ultrasound variables will be included in the model predicting the success of decanulation. Multiple logistic regression with variable selection using the Akaike information criterion (AIC) method will be used. The presence of multicollinearity between variables will also be investigated and the variable eliminated if necessary.

11 Expected results in terms of scientific and professional advances

This study will determine the factors contributing to the success of decanulation in patients admitted to DIFFICULT-TO-WEAN UNIT after a prolonged ICU stay. The evaluation of these success factors will provide data that is still lacking due to the lack of literature in specialised post-resuscitation ventilatory weaning facilities.

This information may be useful in the post-resuscitation follow-up and in the prioritisation or not of early rehabilitation in these patients.

12 Expected benefits and risks for patients

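### Nothing in section 10.3 ensures that prone sessions, curarisation and ECMO are adjusted for the reason for ICU admission, so a marker of diagnosis could be reported as an independent factor

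*Combined protocol and SAP*

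**What the plan says.** Among the severity factors of the ICU stay, section 4.1 (Main outcome) names "Curarisation or not with duration", "Whether or not prone sessions were performed with duration" and "Whether or not ECMO was used as a back-up". The IGS2 score is in the same group. The reason for ICU admission appears in none of the four groups of factors in 4.1.

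Section 9.2.2 does collect it at inclusion, in an item that begins "Reason for admission to intensive care: acute respiratory failure (ARF), ARF on chronic respiratory failure (CRF), cardiogenic shock, septic shock" and runs to 12 headings, ending with stroke, burns, pancreatitis and coma.

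Section 10.3 sets the selection in two steps. First, "The variables collected will be compared between the 2 groups by the appropriate tests according to the type of variables", and the results serve to "select the variables showing a difference between the 2 groups (p < 0.20) for inclusion in the multivariate logistic regression". Then, "Multiple logistic regression with variable selection using the Akaike information criterion (AIC) method will be used". No section groups the 12 reasons, retains any term for adjustment, or says whether 4.1 or 9.2.2 defines the candidates. The two lists differ in the other direction too: curarisation is a factor in 4.1 but is not itemised in 9.2.2.

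Section 2 states the hypothesis that severity, invasive ventilation, respiratory and extra-respiratory status "are independent factors for successful decanulation". Section 10.1 plans for six variables in the final model.

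**The concern.** Whether a patient was proned, curarised or put on ECMO plausibly depends on why that patient was in intensive care: one would expect a patient with acute respiratory failure to be proned more often than one with stroke. If the underlying problem also affects the chance of decannulation, the treatment and the outcome are associated even when the treatment has no effect of its own. Only a model that holds the reason for admission can separate the two.

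The plan has two routes by which the reason can be missing from that model. It may never be a candidate, if 4.1 is taken as the full list. Or it may be a candidate and lose to its own proxy, because it costs many coefficients and the treatment costs one. At stake is the wording of the main result: proning, curarisation or ECMO could be listed as an independent factor when the real contrast is between types of patient.

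**Working it through.** **The plan's own figure.** Section 10.1 takes 10 events per variable, 6 variables and 60% success: 6 × 10 / 0.60 = 100 patients. This reproduces the stated number, with successes counted as the events.

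**The price of the reason for admission.** 12 headings coded as one factor give 12 − 1 = 11 coefficients. AIC charges 2 per coefficient, so the factor stays only if twice its gain in log-likelihood exceeds 2 × 11 = 22. A yes/no treatment needs a gain above 2. On the chi-square scale these thresholds correspond to p of about 0.024 (11 degrees of freedom) and 0.157 (1 degree of freedom). A three-group reason has 2 coefficients and a threshold of 4, or p of about 0.135. The 12-level coding thus faces a much stricter test than the treatment that stands in for it.

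**The term budget.** By the plan's rule, six variables plus all 11 coefficients would need 17 × 10 / 0.60 = 283.3, so 284 patients. Six plus two would need 8 × 10 / 0.60 = 133.3, so 134. Two coefficients counted within the six leave the requirement at 100.

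**Simulation: inputs.** From the plan: n = 100, about 60% success, screening at p < 0.20, AIC selection, 5% significance. Assumed, because the documents give no figures: 42% of admissions respiratory and 17% neurological; success 70-80% in respiratory, 35-40% in neurological and 50-57% in other patients; 60-80% of patients with acute respiratory failure proned (26-33% overall); prone with no effect of its own. The simulation was repeated with somewhat different splits of the 12 reasons, mostly with 1,500 studies per scenario.

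**Simulation: how often the null prone effect is significant at 5%.**

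| Treatment of the reason for admission | Studies with prone significant |
|---|---|
| Not a candidate (4.1 list only) | about 11-60% |
| One 12-level factor through p < 0.20 and AIC | about 8-30% |
| Three groups, ordinary candidate | about 3-9% |
| Three groups, kept in the model | about 3-5% |

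In the second row, the 12-level reason survived selection in 19-61% of studies, depending on the scenario.

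**Sensitivity to the assumptions.**

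- Separate coding: in a smaller set (600 studies per scenario) with the reasons as separate yes/no items, prone was significant in 6-14.5%, against 17-70% in the same set with the reason absent.
- One binary diagnosis, present in half the patients (3,000 studies per scenario), prone used in 70% with it and 10% without, odds ratio for success 2 to 5: significant in 16-62% if the diagnosis is omitted and 4-8% if it is a candidate.
- Weaker link (prone 50% against 20%, odds ratio 2 to 4): 7-17% if omitted, 3-5% if a candidate.
- No link between diagnosis and outcome: 5% even when the diagnosis is omitted. The excess therefore comes from confounding by the diagnosis, not from the selection procedure alone.

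**The case against.** The strongest reply is that 10.3 screens the variables collected, without limiting them to 4.1. Read literally, the reason for admission is a candidate, and so is the medical history in 9.2.2, which includes neurological and chronic respiratory disease. This stands. A reader might infer from 4.1 that the treatments are analysed without the reason for admission; the documents do not support that. The figures of up to about 60% apply only to the narrower reading.

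Nor does 9.2.2 say that the reasons form one mutually exclusive factor. A patient could have septic shock and acute respiratory failure, and separate yes/no items would each cost a penalty of 2, not 22. This also stands, and it reduces the inflation. It does not remove it in every scenario, and the coding is left open.

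A further reply is that the objective concerns association, that 10.1 and 10.3 speak of prediction, and that 4.1 calls these treatments severity factors. In a purely predictive model a proxy is legitimate. But section 2 speaks of independent factors, and section 12.2 hopes the results may inform therapeutic conduct, so the wording of the result matters. A reader might go further and infer that the study will claim proning affects decannulation; no section says so.

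IGS2 gives some adjustment for severity, but it is not a diagnosis and nothing keeps it in the model.

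Finally, the simulated outcome differed by the same three groups that the remedy uses, so the return to about 5% with grouping is partly built in. Only prone was simulated, not curarisation or ECMO.

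**Conclusion.** The point holds as a gap in the analysis specification, not in data collection. Under either reading of the candidate set, the plan does not ensure that the reason for admission is in a model that reports prone sessions, curarisation or ECMO. A false independent prone factor then arises in about 11-60% of studies with the 4.1 list alone and about 8-30% with a 12-level reason, against about 3-9% once the reason is grouped.

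These sizes rest on an assumed case mix, assumed success rates by group and an assumed link between diagnosis and proning. They fall if the link is weaker or the reasons are coded separately. Extending them to curarisation and ECMO is by analogy.

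Two stronger conclusions are tempting. One is that AIC will usually discard the reason; survival in 19-61% of studies supports often, not usually. The other is that age must also be forced into the model because 4.1 omits it; no calculation here supports that.

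**What to change.** In section 10.3:

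1. State that the reason for ICU admission belongs to the candidate set, and whether 4.1 or 9.2.2 defines the rest of that set.
2. Group the 12 reasons before the analysis into a few categories agreed with the clinicians, for example respiratory, neurological and other. Check that the grouping also suits ECMO, since cardiogenic shock would fall under other in this example.
3. Keep the grouped term in any model that retains prone sessions, curarisation or ECMO, whatever its own p value or AIC contribution.
4. Count its two coefficients within the six terms of section 10.1.
5. If this is not done, describe these three treatments as markers and not as independent factors.

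The change is to wording only, since the reason is already collected. The cost is that up to two of the six planned terms go to adjustment, which leaves four for selected factors. Most of the gain comes from the grouping. Keeping the term adds less, but it guarantees that no estimate for these treatments is reported without it.

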9.3 End of research visit

The end-of-research visit will be carried out when the patient is discharged from the DIFFICULT-TO-WEAN UNIT. The necessary additional information will be collected from the patient's computerised medical record.

The variables collected are :

- Time to spontaneous ventilation (days);
- Time to 1st attempt at de-ventilation (days);
- Time to 24-hour de-ventilation (days);
- Time between 24-hour deventilation and successful final decanulation (days);
- Number of decanulations performed;
- Performance of a decanulation bronchial fibroscopy (yes/no) with abnormalities observed:
 - o pharyngeal oedema ;
 - o unilateral vocal cord paralysis;
 - o Bilateral vocal cord paralysis;
 - o unilateral arytenoid palsy
 - o bilateral arytenoid palsy;
 - o Tracheal ring fracture;
 - o No abnormality observed.
- Number of VAPs in DIFFICULT-TO-WEAN UNIT ;
- Total duration of antibiotic therapy (days) ;
- MRC score;
- Presence of undernutrition (severe/moderate/minimal/no);
- Presence of a nasogastric tube (yes/no);
- Presence of a percutaneous gastrostomy (yes/no);
- Oral feeding resumed (yes/no);
- Mode of discharge (return to intensive care, return home, death).

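### One candidate factor for successful decannulation is defined by that success, and four other in-stay factors depend on patient progress or time at risk

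*Combined protocol and SAP*

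**What the plan says.** The main objective (3.1) is to "determine the factors associated with successful decanulation in tracheostomised patients admitted to the Difficult-to-Wean Unit". Section 4.1 lists 21 candidate factors in four groups. One of the ventilatory factors is "Time from 24-hour deventilation to successful DIFFICULT-TO-WEAN UNIT decanulation (days". The end-of-research list in 9.3 collects the same interval as "Time between 24-hour deventilation and successful final decanulation (days", along with "Number of decanulations performed" and "Performance of a decanulation bronchial fibroscopy (yes/no) with abnormalities observed".

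Section 10.3 divides patients into success and failure of decannulation. It continues: "The variables collected will be compared between the 2 groups by the appropriate tests". Variables with p < 0.20 go forward to a logistic regression with AIC selection. No candidate is excluded on grounds of timing or definition.

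Section 10 does not say which patients make up the two groups, or whether a never-decannulated patient is a failure. It does not say which attempt counts when there are several, from what moment success is being predicted, or how missing values are treated. Elsewhere, 4.2 counts success among all included patients, and 10.1 applies a 60% success rate to 100 subjects.

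**The concern.** An explanatory variable has to be observable in both outcome groups and known before the outcome. The interval to successful decannulation fails the first condition: it ends at the success it is meant to explain.

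Three further candidates are observed only once a patient reaches a step on the way to decannulation: time to the first de-ventilation attempt, time to 24-hour de-ventilation, and fibroscopy abnormalities before decannulation. A fourth, the number of VAPs in the unit, exists for everyone but accumulates over the stay.

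At stake is the primary result. A model that includes the step-dependent variables and drops incomplete cases would lose the patients who never progressed. It would then describe a fitter group than the admitted patients named in 3.1, and could report steps on the path to decannulation as its determinants.

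**Working it through.** **The plan's own figure.** Inputs from 10.1: 6 variables, 10 events per variable, 60% success. 6 × 10 / 0.60 = 100, as stated. Applied to 100 included patients, this gives 60 successes and 100 − 60 = 40 failures, or 40 / 6 = 6.7 failures per planned variable.

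**The outcome-defined factor under each possible reading.**
- All included patients, success versus never successful: at most 60 values among successes and 0 of 40 among failures. A complete-case model containing it has one outcome class and cannot be fitted.
- Decannulated patients only: those who never succeed still have no value.
- First attempt classified: a patient who fails first and succeeds later has a value, but it includes time after the outcome.

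None of these gives a valid comparison.

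**Timing of the 21 factors in 4.1.**

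| Group | Listed | Known at or before unit admission | Later or unclear |
|---|---|---|---|
| ICU severity | 7 | 7 | 0 |
| Ventilatory | 7 | 3 | 4 |
| Respiratory | 3 | 2 | 1 |
| Extra-respiratory | 4 | 3 | 1 |
| Total | 21 | 15 | 6 |

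The six are time to successful decannulation, the two de-ventilation times, in-unit VAPs, fibroscopy abnormalities and the swallowing score. Swallowing is unclear because its timing differs: 4.1 ties it to 6 hours of ventilation, 7.5 to tolerance of several hours off the ventilator, and 9.2.2 and 9.5 to inclusion.

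**Who lacks a value, if all included patients are analysed.** Under 7.7, the cannula is removed only after progressive de-ventilation, plugging and fibroscopy. If that is followed, a success has passed every step, so patients without a value are failures. Because 9.3 records fibroscopy as done or not done, an occasional success without one is possible; hence essentially all, not all.

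**Complete-case loss.** The documents give neither a missing-data rule nor the share of non-progressors. Complete-case analysis and the values of m below are therefore assumptions. With m failures lost:

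| m | Failures left, 40 − m | Per planned variable, (40 − m)/6 | Success share, 60/(100 − m) |
|---|---|---|---|
| 0 | 40 | 6.7 | 60% |
| 10 | 30 | 5.0 | 67% |
| 20 | 20 | 3.3 | 75% |
| 30 | 10 | 1.7 | 86% |

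**Decannulated patients only.** Assume 60 successes and that the 2 to 25% failure rate cited in section 1 applies. At 2%, 60 / 0.98 = 61.2 patients with 1.2 failures; at 25%, 60 / 0.75 = 80 patients with 20 failures. That is 0.2 to 3.3 failures per variable for 6 variables.

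**The case against.** The strongest reply is that the analysis set can largely be inferred, that the sponsor chose these factors deliberately, and that later factors can be analysed properly. Much of this stands. Sections 3.1, 4.2 and 10.1 do point to all included patients, and the reading used here relies on them. A landmark or time-to-event model could use the later factors, and a model of decannulated patients could use values that precede decannulation. It is also fair that, if failures are left blank, the outcome-defined factor fails visibly at the screen. None of this rescues that factor, and 10.3 describes none of these alternative analyses.

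Some stronger readings are not supported:
- A reader might infer that silence on the analysis set is what makes the four other factors invalid. It is not. The difficulty is when and in whom they are measured, and it depends on the all-included reading.
- A reader might expect failures to be given a code, so that the variable separates the groups almost perfectly. The plan proposes no such coding, so no p-value is claimed.
- A reader might link 10.3 to the words "The variables collected are" in 9.3 and conclude that items such as "Mode of discharge (return to intensive care, return home, death" will be screened. The shared phrase is thin evidence, since 4.1 also describes its own factors as collected. Excluding discharge items explicitly settles the matter.
- A reader might assume a direction or size of bias for VAPs. The documents give no rate or duration by outcome.

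The admission factors are not free of missing values either: some patients arrive sedated (9.1.2), and CAM-ICU needs a responsive patient (Appendix 1). That is a separate matter and no reason to keep the step-dependent factors.

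**Conclusion.** The plan is wrong as written on one factor. Time from 24-hour de-ventilation to successful decannulation is defined by the outcome and cannot validly be screened or modelled under any analysis set. This rests on the definitions in 4.1 and 9.3 alone.

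The wider point is conditional. If all included patients are modelled, as three sections imply, the two de-ventilation times and fibroscopy abnormalities are missing selectively among failures, and the VAP count depends on exposure. The tabulated losses illustrate the possible size; they assume complete-case analysis and 10 to 30 non-progressors among the 40 failures. They show how quickly an already modest 6.7 failures per variable can shrink, and do not predict what will happen. The four factors are unsuitable as primary candidates in that model, but may be used in an analysis designed for them.

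**What to change.** - **Remove the factor.** Take time to successful decannulation out of the candidates in 4.1 and 10.3, and describe it in successes only.
- **State the set and classes.** In 10.3, say that the primary set is all included patients, that never-decannulated patients are failures, and which attempt is classified. Use the 48-hour definition in 4.1: a patient recannulated after 48 hours is a success by that definition but could be a failure by status at discharge.
- **State time zero.** Set it at unit admission and limit the primary candidates to the 15 factors in 4.1 known by then. Exclude discharge measurements. Do not enlarge the list with other inclusion data, since only about 40 failures are expected.
- **Place the in-stay factors.** Report the two de-ventilation times, fibroscopy findings and in-unit VAPs (per ventilated day) descriptively, or in a labelled exploratory landmark, time-to-event or decannulated-only analysis. The last may hold as few as about 1 failure, and about 20 at most, under the assumptions above.
- **Reconcile swallowing.** Align its timing across 4.1, 7.5, 9.2.2 and 9.5, and keep it as a primary candidate only if it is measured at admission.
- **Apply the same restriction to the weaning-success model (4.2).** It uses the same factors, and 24-hour de-ventilation as recorded in 7.7 is essentially the same 48-hour event as weaning success.

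No new data are needed. The cost is that in-stay progress variables leave the primary model, and an amendment may have to go to the ethics committee (13.5).
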